5.1.1.4.3 Clinical Laboratory Assessments

Clinical laboratory assessments will be summarized by treatment group for the safety population as shown in [Table 5-19](#).

Table 5-19 Clinical Laboratory Summaries

Endpoint	Description	Timing	Methodology
Descriptives	Summary by laboratory category, parameter and analysis visit 
 Parameters specified in Table 6-22 	Cycle 1: Study baseline (screening), Week 12 (for Cohorts 6C and 6D only), and Week 24 Cycle 2: Cycle baseline and Week 12R	CFB descriptives

5.1.1.4.4 Vital Signs

Vital signs will be summarized by treatment group for the safety population as shown in [Table 5-20](#).

Table 5-20 Vital Signs Summaries

Endpoint	Description	Timing	Methodology
Descriptives	Summary by parameter and analysis visit 
 Parameters specified in Table 6-23 	Cycle 1: Study baseline and Weeks 1, 8, 12 (for Cohorts 6C and 6D only), and 24 Cycle 2: Cycle baseline, Day 1R, and Week 12R	CFB descriptives

5.1.1.4.5 Other Safety Analyses

5.1.1.4.5.1 Best-Corrected Visual Acuity

Manifest refraction will be performed at screening and used for BCVA at all subsequent visits until study exit. If there is a decrease in BCVA, the manifest refraction should be repeated as confirmation. Visual acuity (in Snellen equivalents) will be measured for each eye using a logarithmic visual acuity chart for testing at 10 feet (3 meters) at the scheduled visits.

The visual acuity will be recorded on the eCRF in Snellen equivalent units (eg, 20/63) as the lowest line read with 1 or 0 mistakes.

The line CFB at each evaluation is calculated using the following algorithm:

line change = (10)*[log₁₀ (XB/20) - log₁₀ (XF/20)], where

- XB = denominator of the Snellen equivalent unit at baseline
- XF = denominator of the Snellen equivalent unit at post treatment visit

Each logarithmic value is to be rounded to the nearest tenth before subtraction. A positive value indicates an improvement and a negative value indicates a worsening. For example, the line change for a Snellen equivalent unit of 20/25 at baseline followed by a Snellen equivalent unit of 20/80 at day 2 would be

$$\text{Line change} = 10 \times [\log_{10}(25/20) - \log_{10}(80/20)] = 10 \times (0.1 - 0.6) = -5$$

which represents a worsening of 5 lines in visual acuity.

BCVA will be summarized by treatment group for the safety population as shown in [Table 5-21](#).

Table 5-21 BCVA Summaries

Endpoint	Description	Timing	Methodology
Line CFB ^a	Summary by analysis visit and line change categories defined below or line change of ≤ -2 , -1 , 0 , $+1$, or $\geq +2$: 
 • Better (line changes of $\geq +2$) • No change (line changes of -1, 0, $+1$) 
 ○ Line change of $+1$ ○ Line change of 0 ○ Line change of -1 • Worse (line changes of ≤ -2) 	Cycle 1: Day 2 and Weeks 1, 2, 4, 8, 12, and 24 Cycle 2: Day 1R and Weeks 1R, 4R, 8R, and 12R	Categorical descriptives

CFB = change from baseline

^a All BCVA will be listed.

5.1.1.4.5.2 Macroscopic Bulbar Hyperemia

The macroscopic (gross) bulbar hyperemia grading consists of global assessments and regional assessments, which will be done under consistent illumination by comparing the appearance of the bulbar conjunctiva to standard photographs (Allergan bulbar conjunctival hyperemia grading guide) at the scheduled visits. Regional assessment includes superior temporal, superior nasal, inferior temporal, and inferior nasal assessment. It will be graded using a 5-point scale described as follows:

0	(None)	=	Normal; vessels of bulbar conjunctiva easily observed
+0.5	(Trace)	=	Trace flush, reddish-pink color
+1	(Mild)	=	Mild flush, reddish color
+2	(Moderate)	=	Bright red color
+3	(Severe)	=	Deep, bright diffuse redness

Macroscopic bulbar hyperemia will be summarized by treatment group for the safety population as shown in [Table 5-22](#).

Table 5-22 Macroscopic Bulbar Hyperemia Summaries

Endpoint	Description	Timing	Methodology
Global assessment: severity grade	Summary by analysis visit	Cycle 1: Study baseline (Day 1), Day 2, and Weeks 1, 2, 4, 8, 12, and 24 Cycle 2: Cycle baseline, Day 1R, and Weeks 1R, 4R, 8R, and 12R	Categorical descriptives

5.1.1.4.5.3 Slit-lamp Biomicroscopy

Slit-lamp biomicroscopy will be summarized by treatment group for the safety population. Biomicroscopy findings will be coded using MedDRA terminology and summarized for each eye by treatment group as shown in [Table 5-23](#).

Table 5-23 Slit-lamp Biomicroscopy Summaries

Endpoint	Description	Timing	Methodology
One or more severity grade increase from baseline	Overall summary and by PT	From treatment start date until Week 24/Week 12R or early termination date, whichever comes first	Categorical descriptives

PT = preferred term

5.1.1.4.5.4 Dilated Ophthalmic Examinations

Ophthalmoscopy findings will be coded using MedDRA terminology.

Cup/disc ratio will be reported using a 0.0 to 1.0 scale. The Armaly chart provided by Allergan provides a pictorial scale of cup/disc ratio of 0.0 to 0.8. Only listing will be provided for cup/disc ratio.

Dilated ophthalmic examinations will be summarized by treatment group for the safety population as shown in [Table 5-24](#).

Table 5-24 Dilated Ophthalmic Examinations Summaries

Endpoint	Description	Timing	Methodology
One or more severity grade increase from baseline	Overall summary and by PT	Week 12 (for Cohorts 6C and 6D only), Week 24/Week 12R or early termination date, whichever comes first	Categorical descriptives

PT = preferred term

5.1.1.4.5.5 Photographic Conjunctival Hyperemia

The photographic conjunctival hyperemia grading consists of global assessments and regional assessments, which will be done using a Canfield camera in each eye at the scheduled visits. Global assessment includes global, global nasal and global temporal assessment, and regional assessment includes superior temporal, superior nasal, inferior temporal, and inferior nasal assessment. It will be graded as 0 = none, +0.5 = trace, +1 = mild, +2 = moderate, +3 = severe, CG = cannot grade, and NE = not evaluated.

Photographic conjunctival hyperemia will be summarized by treatment group for the safety population as shown in [Table 5-25](#).

Table 5-25 Photographic Conjunctival Hyperemia Summaries

Endpoint	Description	Timing	Methodology
Global assessment: severity grade	Summary by analysis visit	Cycle 1: Study baseline (Day 1), Day 2, and Weeks 1, 2, 4, 8, 12, and 24 Cycle 2: Cycle baseline, Day 1R, and Weeks 1R, 4R, 8R, and 12R	Categorical descriptives

5.1.1.4.5.6 Intraocular Pressure

Measurement of intraocular pressure (IOP) will be taken for each eye using the Goldmann applanation tonometer affixed to a slit lamp at the scheduled visits.

IOP will be summarized by treatment group for the safety population as shown in [Table 5-26](#).

Table 5-26 Intraocular Pressure Summaries

Endpoint	Description	Timing	Methodology
IOP ^a	Summary by analysis visit	Cycle 1: Study baseline (Day 1), Week 12 (for Cohorts 6C and 6D only), and Week 24 Cycle 2: Cycle baseline, Week 12R	CFB descriptives

IOP = intraocular pressure

^a All IOP data will be listed.

5.1.1.4.5.7 REFRESH PLUS Use

REFRESH PLUS use will be summarized by treatment group for the safety population as shown in [Table 5-27](#).

Table 5-27 REFRESH PLUS Use and Compliance Summaries

Endpoint	Description	Timing	Methodology
REFRESH PLUS descriptives	Summary by analysis visit	Cycle 1: Study baseline (Day 1), Day 2, and Weeks 1, 2, 4, 8, 12, and 24 Cycle 2: Cycle baseline, Day 1R, and Weeks 1R, 4R, 8R, and 12R	CFB descriptives

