5.10 Retreatment

In stage 1 of the study, patients in cohorts 6C and 6D will be retreated (at week 12) [REDACTED]

[REDACTED]

[REDACTED]

[REDACTED]

[REDACTED]

To help guide the investigator's decision on retreatment, [REDACTED] unless a $\geq +2$ hyperemia grade [REDACTED] is present, at which time the investigator may elect not to retreat the patient in stage 1. In this case, the

Approval Date: 19-Jan-2017

patient will not be retreated in either eye but continue to be observed for safety (see Table 3) for the duration of the study. [REDACTED]

For stage 2, patients in treatment groups 2 and 3 will be retreated (at week 12) with CFI in both eyes at the same dose used for the baseline (day 1) [REDACTED] Treatment group 1 patients will be retreated at week 12 with vehicle. If retreatment is not administered, the patient will continue to be observed for safety (see Table 4) and exited at the Week 24/Week 12R/Exit visit.

In stage 2, the investigator can elect to [REDACTED] if a $\geq +2$ hyperemia grade [REDACTED] is present. [REDACTED]

[REDACTED]

[REDACTED]

6 Response Measures and Summary of Data Collection Methods

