5.1.1.1.3 Statistical Methodology

The methodologies defined in Table 5-2 apply as specified to individual endpoints defined in this SAP for stage 1.

Table 5-2 Statistical Methodology – Stage 1

Methodology	Description
Categorical counts	
 • Number of patients in individual categories 
 ○ Patients with ≥ 1 qualifying event counted once per individual category
Categorical descriptives	
 • Number and percentage of patients in individual categories 
 ○ Patients with ≥ 1 qualifying event counted once per individual category • N1 if percentage denominator \neq number of patients in the population (standard percentage denominator) 
 ○ N1 = patients with nonmissing value
Continuous descriptives	
 • N1, mean, SD, median, minimum, maximum • N1 = patients with nonmissing value
CFB descriptives	
 • Continuous descriptives for baseline, postbaseline, and CFB values • N1 = patients with nonmissing values at both baseline and the specified postbaseline analysis visit
Responder	
 • Categorical descriptives for responders and nonresponders • N1 = patients with nonmissing values at both baseline and the specified postbaseline analysis visit

CFB = change from baseline

Two treatment cycles are defined in this analysis plan. Treatment Cycle 1 includes all visits from study baseline (also called cycle 1 baseline) to Week 24 or Exit visit if a patient receives ██████████ throughout the study, or to the last visit before retreatment if a patient receives ██████████ during the study. For visits in treatment Cycle 1, refer to study windows in Section 6.2. Treatment Cycle 2 applies to patients who receive retreatment, and includes all visits from retreatment and thereafter. Visits in treatment Cycle 2 will be determined based on the study days relative to the retreatment visit using the study windows specified in Section 6.2.

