The study baseline value of an assessment will be the measurement prior to the treatment at Day 1 unless it is missing. In that case, the last nonmissing value recorded prior to the treatment (Day 1) will be used instead. The cycle baseline (also called cycle 2 baseline) value of an assessment will be the measurement prior to the retreatment at Week 12 from the first treatment unless it is missing. In that case, the last nonmissing value recorded prior to the retreatment (Week 12) will be used instead.

Ocular evaluation will be summarized by study eye and contralateral eye separately.

Some raw and derived data listings will be provided, and will be fully defined in the table, figure, and data listing specification document.

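### The two hyperemia tables count eyes by grade at each visit but do not show how many eyes worsened from baseline, or whether a grade of +2 or higher is new

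*SAP*

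**What the plan says.** SAP section 5.1.1.4.5 gives Tables 5-22 and 5-25 the same single endpoint, "Global assessment: severity grade", by analysis visit, using categorical descriptives. Section 5.1.1.1.3 defines that method as "Number and percentage of patients in individual categories". The same section defines a change-from-baseline method, "Continuous descriptives for baseline, postbaseline, and CFB values", which neither hyperemia table uses. Study baseline and cycle baseline appear in both tables as visits. For the unit of summary, the SAP states "Ocular evaluation will be summarized by study eye and contralateral eye separately".

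The other main objective safety measures are compared with baseline. BCVA is tabulated as line change; IOP, vital signs and laboratory values get change-from-baseline descriptives; slit lamp (Table 5-23) and dilated examination (Table 5-24) use "One or more severity grade increase from baseline". For slit lamp, "Biomicroscopy findings will be coded using MedDRA terminology and summarized for each eye by treatment group", and Table 6-24 includes bulbar or palpebral conjunctival hyperemia on levels 0, +0.5, +1, +2 and +3.

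The graders differ. Protocol 11.1.9 gives the global macroscopic grade to the follow-up investigator, who is masked under 5.3. Protocol 11.1.10 sends the photographs to a reading center. Protocol 5.3 gives the slit-lamp conjunctiva to the treating investigator, who also administers study treatment.

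Protocol 5.10 refers to a hyperemia grade of +2 or higher being present, "at which time the investigator may elect not to retreat the patient in stage 1". The text around that criterion is redacted.

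**The concern.** Stage 1 is a dose escalation with safety among its objectives, and its analyses are meant to support the design of later studies. For a local ocular treatment, a natural safety question about redness is how many eyes became redder than they were before dosing. A count of eyes at each grade does not answer it. Patients have moderate to severe dry eye, so some eyes may plausibly be red on Day 1; an eye at +2 in Week 4 may have started there or may have reached it after treatment. Eyes that worsen and eyes that improve also offset each other in the counts.

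The omission falls on the two hyperemia grades made by someone other than the treating investigator. Within-eye worsening is tabulated only for the grade made by the person who gives the treatment.

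**Working it through.** **Inputs.** Stage 1 cohort sizes (SAP 5.1.2): 3 for Cohort 1; 4 each for Cohorts 2, 6C and 6D; 8 each for Cohorts 3 through 6B. Sum: 3 + 3 × 4 + 6 × 8 = 63 over 10 cohorts, matching the stated maximum. Each patient contributes one study eye and one contralateral eye, tabulated separately, so a full cohort has 8 or 4 eyes per panel in nine of the ten cohorts. The documents contain no observed grades, so the counts below are illustrations.

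**What the counts allow.** Let n be the eyes in a panel, m0 the number at +2 or higher at baseline, and m1 the number at +2 or higher at a later visit, with the same eyes observed at both. The number newly at +2 or higher (below +2 at baseline) must lie between

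- lower limit: max(0, m1 − m0)
- upper limit: min(m1, n − m0)

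| n | m0 | m1 | Lower limit | Upper limit | Newly at +2 or higher |
|---|---|---|---|---|---|
| 8 | 4 | 4 | max(0, 0) = 0 | min(4, 4) = 4 | 0 to 4 |
| 8 | 2 | 2 | max(0, 0) = 0 | min(2, 6) = 2 | 0 to 2 |
| 8 | 3 | 5 | max(0, 2) = 2 | min(5, 5) = 5 | 2 to 5 |
| 4 | 2 | 2 | max(0, 0) = 0 | min(2, 2) = 2 | 0 to 2 |

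The last row has the planned size of Cohorts 6C and 6D, the two retreatment cohorts. The limits also show what is not lost: m1 is printed, new cases cannot exceed it, and a net rise m1 − m0 is a guaranteed minimum of new cases.

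**Any worsening.** If 3 of 8 eyes go from +0.5 to +2, 3 go from +2 to +0.5 and 2 stay put, the printed distribution is identical at both visits although 3 eyes rose two levels. More generally, with an unchanged distribution of four eyes at +1 and four at +2, up to 4 of 8 could have worsened; with 0, 0.5, 0.5, 1, 1, 1, 2, 2, up to 5 of 8.

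**Does Table 5-23 fill the gap?**

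| Feature | Tables 5-22 and 5-25 | Table 5-23 (slit lamp) |
|---|---|---|
| Grader | Masked follow-up investigator; reading center | Treating investigator (conjunctiva) |
| Timing | Each visit, both cycles | Pooled from treatment start to Week 24/12R or early termination |
| Within-eye comparison | None | Increase of one or more grades |
| Baseline after retreatment | Cycle baseline shown as a visit, not compared | Not stated |
| Size of one grade step | Not applicable | Not defined, although +0.5 is a level |

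It fills the gap only in part.

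**The case against.** The strongest case against has four parts.

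1. Table 5-23 already reports within-eye worsening and covers conjunctival hyperemia. This stands, so the SAP as a whole does not lack a within-eye hyperemia summary. What is missing is one for the two grades made away from the treating investigator, by visit and with a stated baseline in Cycle 2.

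2. Cohorts are small, and SAP 6.2 puts all assessments in listings, so each eye's course can be read by hand. That is true and limits the harm. But a listing is not a summary; BCVA and IOP are listed too and still get a change summary.

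3. A reader might infer that offsetting moves would leave the table showing no effect. The documents do not support that as a general statement. A fully unchanged distribution is uncommon: assuming 8 eyes that each move up or down one level with probability 0.25 (values with no source in the documents), it occurred in 0% to 3% of simulated cohorts in which at least two eyes worsened, across several assumed baseline spreads. The usual problem is that the distribution changes but the number worsened cannot be read from it.

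4. A reader might also infer that the tables hide eyes meeting the retreatment guidance. They do not. The readable text of Protocol 5.10 describes a grade that is present, not a change, and eyes at +2 and +3 are counted directly at Week 12 and cycle baseline. The redaction hides which hyperemia assessment is meant, so any link to these two tables is an inference, and the decision is made per patient by the investigator, not from a cohort table.

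Finally, the table specifications sit in a separate document and may contain a shift table. The SAP, however, names the method for each endpoint, and for these two it names counts only.

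**Conclusion.** The point holds as a reporting gap in the two tables. They give exact counts of eyes at each grade by visit, but not the number that worsened from baseline or are newly at +2 or higher. In a cohort of 8 that uncertainty can be as wide as 0 to 4 eyes, and in a cohort of 4 as wide as 0 to 2, when the count at +2 or higher is the same at both visits. This rests on the SAP's definition of categorical descriptives and on complete data at both visits; how wide the range would be in practice depends on grades not yet seen.

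Stage 1 is descriptive and its size was set empirically, so no alpha, power or estimate changes. The change is worth making because safety is part of the stage 1 objective, the data are already collected, and the SAP does this for its other ocular examinations.

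**What to change.** Add to Tables 5-22 and 5-25, separately for study eye and contralateral eye and by visit, either:

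- a baseline-by-visit shift table of the global grade; or
- n (%) of eyes with an increase of at least one scale level from baseline, and n (%) newly at +2 or higher (below +2 at baseline), with eyes observed at both times as the denominator.

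Define a level as one step on 0, +0.5, +1, +2, +3, so that 0 to +0.5 and +0.5 to +1 each count as one. Use study baseline for Cycle 1, and both study and cycle baseline for Cycle 2. For Table 5-25, state that images that cannot be graded or were not evaluated are excluded from the denominator and counted separately.

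The cost is a short SAP edit, a standard shift-table program and a few extra rows per table. No new data are needed, and the retreatment guidance is untouched.

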6.5.4 Slit-lamp Biomicroscopy

The slit-lamp biomicroscopy examination consists of evaluation of the eye area/condition using a 5-point or 6-point scales, as well as present no or yes, as shown in [Table 6-24](#).

Table 6-24 Slit-lamp Biomicroscopy Scales

Eye Area/Condition	Scale
Eyelids/Eyelid Margins/Lashes	0 (None)
• Edema (eyelids)	+0.5 (Trace)
• Erythema	+1 (Mild)
Conjunctiva (Bulbar or Palpebral)	+2 (Moderate)
• Hyperemia	+3 (Severe)
• Edema	
• Subconjunctival Hemorrhage	
Cornea	
• Edema	
• Superficial Punctate Keratopathy	
Anterior Chamber	0 = 0 cells
• Cells	+0.5 = 1 to 5 cells (trace)
	+1 = 6 to 15 cells

Eye Area/Condition	Scale
	+2 = 16 to 25 cells +3 = 26 to 50 cells +4 = > 50 cells
Anterior Chamber • Flare	0 = None: no flare seen +1 = Faint: faint flare seen +2 = Moderate: iris and lens details clear +3 = Marked: iris and lens details hazy +4 = Intense: fibrin or plastic aqueous
Presence of Iris/Pupil Pathology and Other Pathology	Yes No
Other Pathology if present	+0.5 (trace) +1 (mild) +2 (moderate) +3 (severe)

Explanation:

Eyelids/Eyelid Margins/Lashes

Edema (eyelids)

0	(None)	No edema
+0.5	(Trace)	Localized, minimal (trace) swelling
+1	(Mild)	Localized, mild swelling
+2	(Moderate)	Diffuse, moderate swelling
+3	(Severe)	Diffuse, severe swelling

Erythema

0	(None)	No erythema
+0.5	(Trace)	Localized, minimal (trace) flush reddish color
+1	(Mild)	Localized, mild, flush reddish color
+2	(Moderate)	Diffuse reddish color encompassing the entire lid margin
+3	(Severe)	Deep diffuse reddish color of lid margins and superior and/or inferior eyelid

Conjunctiva (Bulbar or Palpebral)

Hyperemia

0	(None)	No hyperemia
+0.5	(Trace)	Minimal (trace) flush, reddish color
+1	(Mild)	Mild flush, reddish color
+2	(Moderate)	Bright red color
+3	(Severe)	Deep, bright diffuse redness

Edema

0	(None)	No edema
+0.5	(Trace)	Localized, minimal (trace) swelling

+1	(Mild)	Localized, mild swelling
+2	(Moderate)	Diffuse, moderate swelling
+3	(Severe)	Diffuse, severe swelling

Subconjunctival Hemorrhage

0	(None)	No hemorrhage
+0.5	(Trace)	Flat hemorrhage \leq 1 quadrant
+1	(Mild)	Elevated hemorrhage \leq 1 quadrant, or flat and $>$ 1 quadrant
+2	(Moderate)	Elevated hemorrhage $>$ 1 but \leq 2 quadrants
+3	(Severe)	Elevated hemorrhage $>$ 2 quadrants

Cornea**Edema**

0	(None)	No edema
+0.5	(Trace)	Localized, minimal (trace) epithelial haze
+1	(Mild)	Dull glass appearance of epithelium that may include fine localized microcystic changes

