+2	(Moderate)	Dull glass appearance of epithelium with large number of cystic changes with or without stromal edema
+3	(Severe)	Epithelial bullae and/or stromal edema, localized or diffuse, with or without stromal striae

Superficial Punctate Keratopathy

0	=	No superficial punctate keratopathy
+0.5	=	Trace
+1	=	Mild
+2	=	Moderate
+3	=	Severe

Anterior Chamber**Cells**

0	=	0 cells
+0.5	=	1 to 5 cells (trace)
+1	=	6 to 15 cells
+2	=	16 to 25 cells
+3	=	26 to 50 cells
+4	=	$>$ 50 cells

Flare

0	=	None: no flare seen
+1	=	Faint: faint flare seen
+2	=	Moderate: iris and lens details clear
+3	=	Marked: iris and lens details hazy
+4	=	Intense: fibrin or plastic aqueous

Iris/Pupil and Other Pathology

The presence of iris/pupil pathology and any other pathology will be evaluated. Other pathology will be graded as +0.5 = trace, +1 = mild, +2 = moderate, and +3 = severe.

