6.5.5 Dilated Ophthalmic Examinations

The evaluation of dilated ophthalmic examinations is shown in [Table 6-25](#).

Table 6-25 Dilated Ophthalmic Examinations Grade

Description	Grade
Lens Status: 
 • Phakic 
 ○ Cortical lens opacity ○ Nuclear lens opacity ○ Posterior Subcapsular lens opacity • Pseudophakic • Aphakic 	Severity: 
 0 (None) 1 (Mild) 2 (Moderate) 3 (Severe)
Presence of Other Pathology	Yes No
Other pathology if present: 
 • Lens • Vitreous • Fundus • Optic nerve 	+0.5 (Trace) +1 (Mild) +2 (Moderate) +3 (Severe) NE (Not Evaluable)

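### The slit-lamp and dilated-exam tables show only whether a severity grade rose, so for findings other than global hyperemia the planned summaries lose how far it rose

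*SAP*

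**What the plan says.** SAP 5.1.1.4.5.3 (Table 5-23, slit lamp) and 5.1.1.4.5.4 (Table 5-24, dilated examination) each contain a single endpoint row: "One or more severity grade increase from baseline". It is shown overall and by preferred term. For the slit lamp the SAP adds: "Biomicroscopy findings will be coded using MedDRA terminology and summarized for each eye by treatment group". The method in both tables is categorical descriptives, which SAP Table 5-2 defines as number and percentage with the rule "Patients with ≥ 1 qualifying event counted once per individual category". For the slit lamp the window is the whole follow-up, not each visit.

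The underlying data are finer. SAP 6.5.4 describes "evaluation of the eye area/condition using a 5-point or 6-point scales". The top of the edema scale for lids and conjunctiva is "Diffuse, severe swelling". Trace is a level of its own: "Other pathology will be graded as +0.5 = trace, +1 = mild, +2 = moderate, and +3 = severe". SAP 6.5.5 grades cortical and nuclear opacity and "Posterior Subcapsular lens opacity" from 0 to 3.

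Elsewhere the SAP keeps size. Table 5-21 shows visual acuity by category of line change. Tables 5-22 and 5-25 show macroscopic and photographic global hyperemia by severity grade at each visit. SAP 5.1.1.1.3 says that ocular evaluations are reported separately for the study eye and the contralateral eye.

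**The concern.** Safety is part of the Stage 1 objective, and the design is a paired-eye comparison. From Cohort 2 onward one eye receives drug and the other vehicle. The useful safety question is therefore whether drug eyes react more often or more severely than vehicle eyes in the same patients. The planned row addresses only the first half.

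Both eyes undergo the same kind of local procedure; the SAP's exposure definition (Table 5-16) calls it an injection. If the procedure alone often produces a small rise, the percentage with any rise could be high in both eyes, and a difference in severity would not appear in the summary.

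The protocol itself attaches weight to grade. Section 5.10 refers to a hyperemia grade of +2 or more, "at which time the investigator may elect not to retreat the patient in stage 1". That shows that the size of a finding matters in this trial. It does not set a threshold for other findings.

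**Working it through.** **1. Scale lengths (SAP Tables 6-24 and 6-25).**
- Lid, conjunctival and corneal findings: 0, +0.5, +1, +2, +3, so 5 levels.
- Anterior chamber cells: 0, +0.5, +1, +2, +3, +4, so 6 levels.
- Flare: 0, +1, +2, +3, +4, so 5 levels.
- Lens opacity: 0 to 3, so 4 levels.

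This reproduces the SAP's own description of 5- or 6-point slit-lamp scales.

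**2. How many different rises fall into the one category.** A scale with k levels has k(k − 1)/2 possible upward moves.

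| Scale | Upward moves | Counted if a grade is one scale step | Counted if a grade is 1.0 unit |
|---|---|---|---|
| 5 levels with trace | 5 × 4 / 2 = 10 | 10 | 8 |
| Cells | 6 × 5 / 2 = 15 | 15 | 13 |
| Flare | 5 × 4 / 2 = 10 | 10 | 10 |
| Lens opacity | 4 × 3 / 2 = 6 | 6 | 6 |

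The two moves that drop out under the 1.0-unit reading are 0 to +0.5 and +0.5 to +1. Under either reading, 0 to +1 and 0 to +3 give the same yes.

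**3. Does another planned summary show the examination grade?**
- Hyperemia: yes, for the global assessment (Tables 5-22 and 5-25).
- Punctate keratopathy: only indirectly, through the change in corneal fluorescein staining (Table 5-11), which is a different assessment.
- Cells, flare, corneal edema, lid edema and erythema, conjunctival edema, subconjunctival hemorrhage, lens opacity: no.
- Ocular TEAEs by worst severity (Table 5-18): this is severity as defined in Protocol 8.12.3, which rests on how well the event is tolerated and how far it limits activity. A marked sign without symptoms can be a mild event. The row counts patients and does not state a split by eye.
- Listings (SAP 6.2): they hold every assessment, but do not summarize one eye against the other.

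**4. Group sizes.** 3 + 3 × 4 + 6 × 8 = 63, which matches the stated Stage 1 maximum. SAP 5.1.1.1.2 analyzes by treatment group/cohort, so each summary rests on 3, 4 or 8 patients. The F1 cohorts listed there (2, 3, 4, 5A, 6C) sum to 4 + 8 + 8 + 8 + 4 = 32; Cohort 5B is not in that list, and with it the total would be 40.

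**5. Illustration only.** The grade distributions below are assumed; nothing in the documents supports one over the other. Worst rise of none / one / two / three grades, in percent of eyes:
- A. Vehicle 10/60/20/10, drug 5/35/35/25. Any rise: 90% v 95%. Two or more grades: 20 + 10 = 30% v 35 + 25 = 60%. The yes/no row hides most of the contrast.
- B. Vehicle 80/15/4/1, drug 50/40/8/2. Any rise: 20% v 50%. Two or more grades: 4 + 1 = 5% v 8 + 2 = 10%. The yes/no row shows the contrast well.

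As a measure of information, simulated detection with 40 pairs (between-eye correlation 0.5, two-sided 5%, exact McNemar test on yes/no v sign test on full grade) is 4% v 86% in A and 88% v 83% in B. With 8 pairs A gives 0% v 8%. No such test and no pooling of the F1 cohorts is planned, so these figures do not describe the planned analysis.

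**The case against.** Much can be said for the plan as it stands, and several stronger readings fail.

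- **That hyperemia severity is lost.** A reader might infer this from the +2 mention in Protocol 5.10. It is not so: two tables give global hyperemia by grade and visit, and ocular evaluations are split by eye. The text next to that mention is redacted, so it is not known which hyperemia assessment it uses.
- **That a trace and a severe reaction count the same.** This holds if one grade is one scale step, which is the plain reading because trace is listed as a grade. The SAP does not define the term, and under a 1.0-unit reading a rise from none to trace would not count. Lens opacity has no trace level. Mild against severe is the contrast that holds on every scale and both readings.
- **That the row costs a known amount of power.** It does not. Stage 1 is descriptive, and the ordering of the two approaches reverses between illustrations A and B. In a cohort of 8 neither has useful power.
- **That severity disappears from the report.** Grades are listed, and in a cohort of 4 or 8 a reader can scan the listing. Table specifications are in a separate document that is not available here, so a shift table there cannot be excluded.
- **That cohort escalation depends on these tables.** Protocol Section 3 ties it to review after two weeks of monitoring.

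These points stand and lower the priority. They do not remove the gap for the findings other than hyperemia: Protocol 7.3.1 names the SAP as the place where safety methods are described, and the SAP provides no graded summary for them. The argument about a common mild procedural reaction applies mainly to the surface of the eye, so the case for Table 5-24 is weaker.

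**Conclusion.** The point holds in limited form. For anterior chamber cells and flare, corneal edema and punctate keratopathy, lid edema and erythema, conjunctival edema and subconjunctival hemorrhage, and with lower priority lens opacity, the only planned summary of the examination itself merges every counted rise into one category. Adverse event severity and listings do not replace a graded comparison of study and contralateral eyes.

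The conclusion rests on the SAP text alone and assumes that the separate table specifications add nothing. How much would be missed in practice cannot be stated, because it depends on grade distributions that the documents do not give. No planned test or stated sample-size figure is affected. Priority: CONSIDER.

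**What to change.** Keep the existing row in both tables. In Table 5-23 add, for each graded finding and separately for study and contralateral eyes, a shift table of baseline grade by worst postbaseline grade, on the finding's native scale and over the same window as the present row. Do the same in Table 5-24 for lens opacity only.

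A shift table on the native scale needs no definition of one grade, and it does not carry the +2 hyperemia figure over to unrelated scales such as cells or cataract. The existing row still needs its own definition of a grade increase, but that is a separate matter.

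The cost is SAP wording and extra table blocks from grades already collected. The downside is longer tables, with many empty cells and small counts in cohorts of 3 to 8. If power figures are used to support the change, label them as illustration only.
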